#### **14.3.1.6 Patient's assessment of global response to treatment**

Patient's assessment of global response to treatment at 72 hours, Day 8 and Day 15 for the first flare will be evaluated using an analysis of variance including factors for treatment (anakinra 100 mg, anakinra 200 mg and triamcinolone), ULT use (yes, no) and BMI ( $<30.0$ ,  $\geq 30.0$  kg/m^2). The estimated mean global response to treatment for each treatment group (anakinra and triamcinolone), the estimated difference between the groups and the associated 95 % confidence interval and p-value from the model will be presented. Further, the estimated mean global response for each of the 2 anakinra doses (100 mg and 200 mg), the difference of the 2 different anakinra dose groups versus triamcinolone will also be estimated, with corresponding 95 % confidence intervals and p-values.

The observed patient-assessed global response categories at each time point will also be presented by descriptive statistics.

The cumulative proportion of patients that reach good patient's assessed global response to treatment (where good response is defined as good, very good or excellent) over time will be illustrated graphically.

#### **14.3.1.7 Physician's assessment of global response to treatment**

Physician's assessment of global response to treatment at 72 hours, Day 8 and Day 15 for the first flare will be evaluated using an analysis of variance model including factors for treatment (anakinra 100 mg, anakinra 200 mg and triamcinolone), ULT use (yes, no) and BMI ( $<30.0$ ,  $\geq 30.0$  kg/m^2). The estimated mean global response to treatment for each treatment group (anakinra and triamcinolone), the estimated difference between the groups and the associated 95 % confidence interval and p-value from the model will be presented. Further, the difference of the 2 different anakinra dose groups versus triamcinolone will also be estimated, with corresponding 95 % confidence intervals and p-values.

The observed physician-assessed global response categories at each time point will also be presented by descriptive statistics.

The cumulative proportion of patients that reach good physician's assessed global response to treatment (where good response is defined as good, very good or excellent) over time will be illustrated graphically.

#### **14.3.1.8 Physician's assessment of clinical signs**

The investigator will assess the tenderness, swelling and presence of erythema in the index joint.

Physician's assessment of tenderness at 72 hours, Day 8 and Day 15 for the first flare will be evaluated using an analysis of covariance model including factors for treatment (anakinra 100 mg, anakinra 200 mg and triamcinolone), ULT use (yes, no) and BMI ( $<30.0$ ,  $\geq 30.0$  kg/m^2), and baseline tenderness as covariate. The estimated mean tenderness for each treatment group (anakinra and triamcinolone), the estimated difference between the groups and the associated 95 % confidence interval and p-value from the model will be presented. Further, the estimated mean tenderness for each of the 2 anakinra doses (100 mg and 200 mg), the difference of the 2 different anakinra dose groups versus triamcinolone will also be estimated, with corresponding 95 % confidence intervals and p-values. The observed physician-assessed clinical signs categories at each time point will also be presented by descriptive statistics.

Physician's assessment of swelling at 72 hours, Day 8 and Day 15 for the first flare will be evaluated using an analysis of covariance model including factors for treatment (anakinra 100 mg, anakinra 200 mg and triamcinolone), ULT use (yes, no) and BMI ( $<30.0$ ,  $\geq 30.0$  kg/m^2), and baseline swelling as covariate. The estimated mean swelling for each treatment group (anakinra and triamcinolone), the estimated difference between the groups and the associated 95 % confidence interval and p-value from the model will be presented. Further, the estimated mean swelling for each of the 2 anakinra doses (100 mg and 200 mg), the difference of the 2 different

anakinra dose groups versus triamcinolone will also be estimated, with corresponding 95 % confidence intervals and p-values. The observed physician-assessed swelling categories at each time point will also be presented by descriptive statistics.

The presence of erythema at 72 hours, Day 8 and Day 15 for the first flare will be analyzed using a logistic regression model with treatment, ULT use (yes, no) and BMI ( $<30.0$ ,  $\geq 30.0$  kg/m^2) as explanatory variables. The proportion of patients with presence of erythema in each treatment group, the estimated odds ratio of anakinra to triamcinolone, the corresponding 95 % confidence interval and the p-value from the model will be presented. Further, the odds ratios for the comparisons of the 2 different anakinra dose groups versus triamcinolone will also be estimated, with corresponding 95 % confidence intervals and p-values. The observed physician-assessed presence of erythema at each time point will also be presented by descriptive statistics.

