7.5.5.4 Use of rescue medication

Patients who have difficulty in tolerating their pain are allowed to take rescue medication as needed after the 24-hour post-dose pain assessment but not within 6 hours before the 48- and 72-hour post-dose pain assessments.

Rescue medication can be used at the discretion of the investigator and should be prescribed according to the product label; contraindications, interactions and precautions.

Permitted rescue medication includes paracetamol/acetaminophen (up to 1000 mg 4 times daily) and/or codeine (up to 50 mg 4 times daily) or short acting tramadol (up to 100 mg 4 times daily).

Topical ice/cold packs may also be used as rescue therapy.

However, patients will be permitted to continue thrombosis prophylaxis with low dose acetyl salicylic acid (≤ 325 mg/day).

At the discretion of the investigator, patients still having insufficient relief with above drugs after the 72-hour post-dose pain assessment are allowed to take oral prednisone, prednisolone or equivalent at a dose up to 0.5 mg/kg per day for a maximum of 5 days.

Subsequent flares occurring before Day 15 of the latest flare will be treated with permitted rescue medication.

The name, dose, date and time of all rescue medication taken at site will be recorded in the eCRF at Visit 1 to 4 of each flare. Rescue medication taken at home between Visit 1 and 4 of each flare will be recorded in the patient diary.

7.5.5.5 Clinical signs of the most affected joint (index joint tenderness, swelling and erythema)

The investigator will assess the tenderness (on the basis of palpation or passive motion) of the index joint on a 4-point Likert scale (0=no pain, 1=mild/patient states there is pain when touched, 2=moderate/patient states there is pain and winces, 3=severe/patient states there is pain, winces and withdraws).

The investigator will assess the swelling of the index joint on a 4-point Likert scale (0=no swelling, 1=mild swelling, 2=moderate swelling, 3=severe swelling or bulging beyond joint margins).

The investigator will assess erythema of the index joint as either “present” or “absent”.

For each flare, assessments of joint tenderness, swelling and erythema will be performed and recorded in the eCRF at baseline, 72 hours, Day 8 and Day 15.

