9.3.4.7 Physician's assessment of clinical signs

The investigator will assess the tenderness, swelling and presence of erythema in the index joint.

Physician's assessment of tenderness at 72 hours, Day 8 and Day 15 for the first flare will be evaluated using an analysis of covariance model including factors for treatment (anakinra 100

mg, anakinra 200 mg and triamcinolone), ULT use (yes/no) and BMI (<30.0 or ≥ 30.0 kg/m²), and baseline tenderness as covariate. The estimated mean tenderness for each treatment group (anakinra and triamcinolone), the estimated difference between the groups and the associated 95% confidence interval and p-value from the model will be presented. Further, the estimated mean tenderness for each of the two anakinra doses (100 mg and 200 mg), the difference of the two different anakinra treatment groups versus triamcinolone will also be estimated, with corresponding 95% confidence intervals and p-values.

Physician's assessment of swelling at 72 hours, Day 8 and Day 15 for the first flare will be evaluated using an analysis of covariance model including factors for treatment (anakinra 100 mg, anakinra 200 mg and triamcinolone), ULT use (yes/no) and BMI (<30.0 or ≥ 30.0 kg/m²), and baseline swelling as covariate. The estimated mean swelling for each treatment group (anakinra and triamcinolone), the estimated difference between the groups and the associated 95% confidence interval and p-value from the model will be presented. Further, the estimated mean swelling for each of the two anakinra doses (100 mg and 200 mg), the difference of the two different anakinra treatment groups versus triamcinolone will also be estimated, with corresponding 95% confidence intervals and p-values.

The presence of erythema at 72 hours, Day 8 and Day 15 for the first flare will be analyzed using a logistic regression model with treatment, ULT use (yes/no) and BMI (<30.0 or ≥ 30.0 kg/m²) as explanatory variables. The estimated risk of erythema in each treatment group, the estimated odds ratio of anakinra to triamcinolone, the corresponding 95% confidence interval and the p-value from the model will be presented. Further, the odds ratios for the comparisons of the two different anakinra treatment groups versus triamcinolone will also be estimated, with corresponding 95% confidence intervals and p-values.

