#### **14.3.1.9 Inflammatory biomarkers**

The change from baseline in CRP (using the central laboratory value) at 72 hours, Day 8 and Day 15 will be evaluated using an analysis of covariance model including factors for treatment, ULT use (yes, no) and BMI ( $<30.0$ ,  $\geq 30.0$  kg/m^2), and baseline CRP as covariate. The estimated mean change in CRP for each treatment group (anakinra and triamcinolone), the estimated difference between the groups and the associated 95 % confidence interval and p-value from the model will be presented. Further, the estimated mean change in CRP for each of the 2 anakinra doses (100 mg and 200 mg), the estimated differences anakinra 100 mg – triamcinolone and anakinra 200 mg – triamcinolone, and the associated 95 % confidence intervals and p-values from the model will be presented. The observed CRP values at each time point will also be presented by descriptive statistics.

The change from baseline in SAA at 72 hours, Day 8 and Day 15 will be evaluated using an analysis of covariance model including factors for treatment, ULT use (yes, no) and BMI ( $<30.0$ ,  $\geq 30.0$  kg/m^2), and baseline SAA as covariate. The estimated mean change in SAA for each treatment group (anakinra and triamcinolone), the estimated difference between the groups and the associated 95 % confidence interval and p-value from the model will be presented. Further, the estimated mean change in SAA for each of the 2 anakinra doses (100 mg and 200 mg), the estimated differences anakinra 100 mg – triamcinolone and anakinra 200 mg – triamcinolone, and the associated 95 % confidence intervals and p-values from the model will be presented.

The observed SAA values at each time point will also be presented by descriptive statistics.

The evaluation of CRP and SAA at Week 12 will be presented by descriptive statistics.

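### The erythema model leaves out baseline erythema, which is recorded: a valid analysis, but one that gives up some power and leaves chance imbalance uncorrected

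*SAP*

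**What the plan says.** Both documents analyse erythema of the index joint at 72 hours, Day 8 and Day 15 of the first flare with the same terms.

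- SAP 14.3.1.8: "The presence of erythema at 72 hours, Day 8 and Day 15 for the first flare will be analyzed using a logistic regression model". The terms follow: "logistic regression model with treatment, ULT use (yes, no) and BMI".
- Protocol 9.3.4.7: "logistic regression model with treatment, ULT use (yes/no) and BMI". The protocol synopsis gives this rule for secondary binary endpoints in general.

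The other clinical signs in SAP 14.3.1.8 are handled differently. The tenderness model includes treatment, ULT use, BMI "and baseline tenderness as covariate"; the swelling model has the same factors "and baseline swelling as covariate". The next section, 14.3.1.9, models CRP with the same factors "and baseline CRP as covariate", and SAA and SF-36 physical functioning (17.1) follow that pattern.

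The baseline value exists. Protocol 7.5.5.5 says that "assessments of joint tenderness, swelling and erythema will be performed and recorded in the eCRF at baseline, 72 hours", and at Day 8 and Day 15; erythema is scored present or absent. Inclusion criterion 6 requires a tender and swollen index joint and does not mention redness. Randomisation is stratified by ULT use and BMI only (protocol 7.4.4). Neither document gives a reason for the omission or plans a baseline-adjusted erythema analysis; the remaining erythema output is descriptive.

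**The concern.** The modelled outcome is erythema status at a visit, not change in status. A patient whose joint was never red and one whose redness resolved are both counted as having no erythema. Because redness is not required at entry, patients of the first kind can be in the analysis, and baseline status is likely to predict later status well. Leaving out a strong predictor costs precision. It also leaves any chance difference between arms in baseline redness inside the treatment comparison, since neither the stratification nor the model removes it. The plan already avoids this for tenderness and swelling.

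At stake is the precision of one of three clinical signs within the secondary endpoints. The primary analysis is unaffected.

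**Working it through.** **1. The plan's own figure.** No power is stated for erythema. The only power statement concerns the primary VAS endpoint (SAP 7): difference 12 mm, SD 25 mm, two-sided 5%, 80% power, allocation 2:1.

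Controls = (1.960 + 0.842)² × 25² × (1 + 1/2) / 12² = 51.1, so 52, or 156 in total. With the planned 53 and 106, power is 81.4% (normal) or 80.9% (t). The stated 159 reproduces. These arm sizes are used below.

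**2. Power with and without baseline erythema.** These inputs are assumptions, not from the documents: 40% of triamcinolone patients have erythema at 72 hours; the odds ratio given baseline is 0.375; baseline prevalence is 50, 70 or 90%; and 5, 15 or 30% of triamcinolone patients without baseline erythema have it at 72 hours. There were 3,000 simulated trials per cell with 53 per arm, three-level treatment plus ULT use and BMI, and a Wald test of the average anakinra contrast.

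| Baseline prevalence | 5% | 15% | 30% |
|---|---|---|---|
| 50% | 36 → 52 | 58 → 66 | 73 → 75 |
| 70% | 65 → 71 | 70 → 73 | 76 → 76 |
| 90% | 75 → 76 | 75 → 75 | 77 → 77 |

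Columns are the 72-hour rate in baseline-negative controls; entries are power (%) without → with baseline erythema. With no treatment effect, rejection was 4.5 to 5.8% across both models.

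A second assumed set puts 72-hour erythema at 60% (triamcinolone) and 36% (anakinra) in patients red at baseline, and at 6% and 3% in the others. With a Firth fit for the adjusted model, power is 52 → 58, 60 → 65, 68 → 71 and 78 → 79% at 60, 70, 80 and 90% prevalence. An independent simulation gave the same gains of about 6, 5, 3 and 1 points.

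**3. Chance imbalance.** SD of the difference in baseline prevalence = √[p(1 − p)(1/53 + 1/106)].

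- p = 0.5: √(0.25 × 0.0283) = 8.4 points
- p = 0.7: √(0.21 × 0.0283) = 7.7 points
- p = 0.9: √(0.09 × 0.0283) = 5.0 points

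Under the second set of rates, a 10-point imbalance shifts the raw 72-hour difference by 0.10 × (0.60 − 0.06) = 5.4 points at triamcinolone rates, or 0.10 × (0.36 − 0.03) = 3.3 points at anakinra rates.

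**4. Odds ratios, second set.** At 60% prevalence the overall risks are:

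- triamcinolone: 0.6 × 0.60 + 0.4 × 0.06 = 0.384
- anakinra: 0.6 × 0.36 + 0.4 × 0.03 = 0.228

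Marginal odds ratio = (0.228/0.772) / (0.384/0.616) = 0.474. At 70 and 80% prevalence it is 0.453 and 0.430. The planned model returns about 0.46, 0.45 and 0.42, so it recovers its own target. Among patients red at baseline the odds ratio is (0.36/0.64) / (0.60/0.40) = 0.375, which is close to what the adjusted model estimates.

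**5. Sparse data after adjustment, second set.** The probability of no 72-hour event among all baseline-negative patients is [1 − 0.06(1 − p)]^53 × [1 − 0.03(1 − p)]^106. This is about 8, 15 and 28% at p = 0.6, 0.7 and 0.8. An ordinary fit then has no finite estimate for baseline erythema, even though every arm has events.

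**The case against.** The case for leaving the model alone is reasonable. Adjusting for the stratification factors only is valid, and the SAP follows the protocol's rule for binary endpoints, so there is no discrepancy between the documents. The study is an exploratory Phase 2 trial with many secondary endpoints, no multiplicity adjustment and no power claim for erythema. Protocol 5.1.1 lists redness among the features of a flare, and entry needs VAS of at least 50 mm with a tender, swollen joint. Baseline prevalence could therefore be high, and at 90% the gain disappears. All of this stands and limits the point to a minor one.

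Two stronger readings are tempting. A reader might infer that patients without baseline redness pass as treatment successes and so bias the comparison. Randomisation spreads them evenly in expectation, and the simulated type I error stays near 5%, so there is no systematic bias. A reader might also infer that the planned odds ratio is wrongly pulled towards 1. It is nearer 1, but mainly because odds ratios are non-collapsible: the planned model targets the marginal odds ratio and recovers it. The SAP also reports the proportion with erythema per arm beside it, which suits a marginal reading.

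The objection does not supply a reason for treating erythema differently from tenderness and swelling. The descriptive table may show an imbalance but does not correct it.

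**Conclusion.** The omission is real and unexplained, and it departs from how the same section treats the other two signs. Its consequence is lost efficiency and uncorrected chance imbalance on one secondary endpoint. The documents support no claim of bias, of an invalid test, of a protocol–SAP conflict or of any effect on the primary result.

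The size rests entirely on assumed erythema rates. Over the range examined, adjustment adds about 0 to 16 points of power. The gain is largest when baseline redness is mixed and strongly predictive, and there is essentially none when about 90% of patients have it or when it predicts little. A 10-point baseline imbalance is 1.2 to 2 SDs (10/8.4 to 10/5.0); under the second set of rates it would move the raw 72-hour difference by about 3 to 5 points. Severity: minor.

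**What to change.** Before unblinding:

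- Add baseline erythema (present/absent) as an explanatory variable in the erythema model of SAP 14.3.1.8. Amend protocol 9.3.4.7 to match, or list the change in SAP section 5.
- Prespecify a Firth-penalised fit for all three visits, or for any visit at which a treatment group or a baseline-erythema group has no events. A trigger that looks only at treatment arms would miss the situation in step 5.
- State that the reported odds ratio is conditional on baseline erythema. The planned proportions per arm can stay beside it.
- State what happens to a patient whose baseline erythema is missing, since that patient would otherwise drop out of the model.

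The cost is one covariate in an existing model and a few sentences of text, with no new data. Made after unblinding, the same change would look data-driven.

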#### **14.3.1.9 Inflammatory biomarkers**

The change from baseline in CRP (using the central laboratory value) at 72 hours, Day 8 and Day 15 will be evaluated using an analysis of covariance model including factors for treatment, ULT use (yes, no) and BMI ( $<30.0$ ,  $\geq 30.0$  kg/m^2), and baseline CRP as covariate. The estimated mean change in CRP for each treatment group (anakinra and triamcinolone), the estimated difference between the groups and the associated 95 % confidence interval and p-value from the model will be presented. Further, the estimated mean change in CRP for each of the 2 anakinra doses (100 mg and 200 mg), the estimated differences anakinra 100 mg – triamcinolone and anakinra 200 mg – triamcinolone, and the associated 95 % confidence intervals and p-values from the model will be presented. The observed CRP values at each time point will also be presented by descriptive statistics.

The change from baseline in SAA at 72 hours, Day 8 and Day 15 will be evaluated using an analysis of covariance model including factors for treatment, ULT use (yes, no) and BMI ( $<30.0$ ,  $\geq 30.0$  kg/m^2), and baseline SAA as covariate. The estimated mean change in SAA for each treatment group (anakinra and triamcinolone), the estimated difference between the groups and the associated 95 % confidence interval and p-value from the model will be presented. Further, the estimated mean change in SAA for each of the 2 anakinra doses (100 mg and 200 mg), the estimated differences anakinra 100 mg – triamcinolone and anakinra 200 mg – triamcinolone, and the associated 95 % confidence intervals and p-values from the model will be presented.

The observed SAA values at each time point will also be presented by descriptive statistics.

The evaluation of CRP and SAA at Week 12 will be presented by descriptive statistics.

#### **14.3.1.10 Subsequent flares**

The evaluation of efficacy at subsequent flares will be presented by the combined anakinra group, the 2 different anakinra doses (100 mg and 200 mg) and triamcinolone, and by flare, i.e. patient's 2nd flare, 3rd flare, etc. for the ITT population.

Change in patient-assessed pain intensity in the index joint as measured by VAS score from baseline to 24 to 72 hours (average of the assessments performed at 24, 48 and 72 hours) will be estimated using the same mixed model repeated measures analysis as for the primary endpoint.

The estimated mean change from baseline to 24 to 72 hours for each treatment group (anakinra and triamcinolone), the estimated difference between the groups and the associated 95 % confidence interval will be presented for each flare. Graphs will be used to visualize pain intensity (VAS) at each time point for anakinra (combined and each dose group) and triamcinolone estimated from the repeated measures model for each flare. In addition, graphs for each treatment group will be used to visualize pain intensity (VAS) over time for all flares in the same graph.

Patient-assessed pain intensity on VAS will be summarized by descriptive statistics for each time point, i.e. baseline, 6, 12, 18, 24, 36, 48, and 72 hours and Days 5, 6, 7 and 8, as well as the change from baseline at these time points. The presentations will be repeated for patients 2nd flare, 3rd flare, etc.

Patient-assessed pain intensity on Likert will be summarized by descriptive statistics for each time point, i.e. baseline, 6, 12, 18, 24, 36, 48, 72 hours and Days 5, 6, 7 and 8 as well as the change from baseline at these time points. The presentations will be repeated for patients 2nd flare, 3rd flare etc.

Further, the mean pain intensity on both VAS and Likert over time will be visualized graphically. For each treatment group, the mean pain intensity over time will be displayed for each flare.

The number and proportion of responders in the treatment groups at 24, 48 and 72 hours, Day 8 and Day 15 will be summarized by descriptive statistics. The percentage will be based on the number of patients in the ITT population that experienced the specific number of flares.

The number and proportion of patients with onset of effect in the different treatment groups at 6, 12, 24, 48 and 72 hours will be summarized by descriptive statistics. The percentage will be based on the number of patients in the ITT population that experienced the specific number of flares.

The number and proportion of patients with resolution of pain in the treatment groups at 72 hours, Day 8 and Day 15 will be summarized by descriptive statistics. The percentage will be based on the number of patients in the ITT population that experienced the specific number of flares.

The number and proportion of patients that took rescue medication from the first IMP administration at Visit 1 up to and including the Day 15 visit in the treatment groups will be summarized by descriptive statistics. The proportion and number of occasions of rescue medication events and the type of rescue medication will also be presented.

Patient's assessment of global response to treatment at 72 hours, Day 8 and Day 15 will be summarized by descriptive statistics.

Physician's assessment of global response to treatment at 72 hours, Day 8 and Day 15 will be summarized by descriptive statistics.

Physician's assessment of clinical signs (tenderness, swelling and presence erythema) at 72 hours, Day 8 and Day 15 will be summarized by descriptive statistics.

The change from baseline in CRP and SAA at 72 hours, Day 8 and Day 15 will be summarized by descriptive statistics.

